#### 8.2.5 Statistical Analysis Plan

#### **Primary outcome**

PFS will be estimated by the Kaplan-Meier (KM) estimator, and presented with pointwise 90% confidence intervals. An event will be defined as documented progression or death for any cause, subjects without an event will be censored at the last date known to be alive without progression. Left truncation at the time of the start of study treatment will be used to adjust for "immortal time" before study enrollment.

The primary efficacy hypothesis of 12-month PFS exceeding 54% will be evaluated by comparing the KM-estimate to the null-hypothesis values using a one-sided z-test.

The primary outcome will also be summarized separately for subjects with ≤PR, and VGPR at the initiation of treatment. No between-group comparisons will be performed.

#### **Secondary outcomes**

Time-to-event outcomes, such duration of response, time to progression/relapse, progression-free survival, and overall survival will be described using the Kaplan-Meier estimator. Left truncation at the start of study treatment will be used. Best objective response on the trial and negative MRD prevalence at specific timepoints will be summarized as counts with percentages. Quality of life scores will be summarized at each timepoint with descriptive statistics and analyzed using mixed effect models with a random subject intercept.

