Main Exclusion Criteria	
 
Prior exposure to belantamab mafodotin before enrollment on the trial, including before administration of anti-BCMA CAR-T.
 
Evidence of progression/relapse after BCMA CAR-T before enrollment (this requirement is also necessary prior administration of first study drug).
 
Subject has achieved CR/sCR at the time of enrollment (this requirement is also necessary prior to administration of first study drug).
 
Subject was given BCMA CAR-T under EAP (expanded access protocol) for non-conforming product.
 
Subject progressed on a prior anti-BCMA therapy before receiving commercial anti-BCMA CAR-T.
 
Any previous treatment-related adverse events higher than grade 1 at enrollment (except for alopecia and grade 2 neuropathy).
 
Acute active infection requiring treatment within 14 days of enrollment (this requirement is necessary also prior to administration of first study drug).
 
Current or prior involvement of the central nervous system by multiple myeloma.
 
Smoldering multiple myeloma or POEMS.
 
						
Primary Objectives	To describe 12-month progression-free survival (PFS) of patients receiving belantamab mafodotin as maintenance therapy (every eight weeks) after anti-BCMA CAR-T administration for relapsed/refractory myeloma.						
Primary Endpoints	12-month conditional PFS, defined as the probability of being alive without progression/relapse or death at 12 months from the time of CAR-T administration conditional on being alive without progression/relapse at 3 months from the time of CAR-T.						

[figure not shown]
Short Title: MCW EMBRACE TRIAL 7 Version No.: 3
Version Date: 12/29/2022

Secondary Objectives	
 
To describe the toxicity profile of belantamab mafodotin given as maintenance after CAR-T.
 
To describe progression-free survival.
 
To describe changes in International Myeloma Working Group (IMWG) response category for patients not in CR when initiating therapy with belantamab mafodotin as post-CAR-T maintenance.
 
To identify the rate of elimination of minimal residual disease (MRD) (≤10–5) in patients with myeloma at baseline and after starting belantamab mafodotin as post-CAR-T maintenance (at screening/baseline, after two, six, and 12 cycles).
 
Patient-reported quality of life studies (QoL).
 
To describe the overall survival (OS) for the entire cohort from the time of CAR-T administration.
 
					

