#### 1.2 BCMA-directed CAR-T Cells

B-cell maturation antigen (BCMA) is expressed on clonal and polyclonal plasma cells, although the intensity of expression can vary with time (5, 6). Highly prevalent expression on plasma cells and exclusivity to the B-cell lineage has made BCMA an attractive target for multiple myeloma (MM) therapeutics, including chimeric antigen receptor (CAR)-T-cell technology. In a phase 1 study of bb2121, a BCMAtargeting CAR T-cell construct with 4-1BB costimulatory molecule, 33 of the 36 enrolled patients received CAR-T cells after lymphodepleting chemotherapy. (7) ORR was 85%, including a CR rate of 45%. Of the

Short Title: MCW EMBRACE TRIAL 20 Version No.: 3 16 patients with a response who were evaluated for MRD, 15 were MRD negative at 10^-5. Cytokine release syndrome occurred in 76% patients and was grade 3 in 6%. Neurotoxicity occurred in 42% patients, with grade 3 or 4 in 3%. Based on phase II KarMMa study data, Bristol Myers Squibb and bluebird bio, Inc. submitted a biologics license application to the U.S. Food and Drug Administration (FDA) for bb2121 (idecabtagene vicleucel [ide-cel]) on March 31, 2020 for treatment of myeloma patients who have received at least four prior lines of therapy, including immunomodulatory agent (IMiD), proteasome inhibitor (PI) and anti-CD38 antibody.

Available data from clinical studies demonstrate that peak expansion of BCMA-directed CAR-T cells generally correlates with response, whereas the extent of baseline BCMA expression does not, although most MM cells express BCMA.(8-10) BCMA expression on residual MM cells generally decreases after CAR T-cell therapy, more so in responders than in non-responders. At the time of progression, an increase in BCMA expression has been observed, potentially suggesting that additional BCMA-targeted therapies may be a future treatment option. Another postulated mechanism of disease progression is the lack of long-term persistence of CAR-T cells. Persistence of CAR-T cells has ranged from a few days in most patients to a few months in some patients, with some variability across studies. In a phase I study of bb2121, 96%, 86%, 57%, and 20% patients had detectable CAR-T cells at one, three, six, and 12 months, respectively. (7)

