#### 2.3 Secondary Objectives

- 1. To describe the toxicity profile of belantamab mafodotin given as maintenance after CAR-T.
- 2. To describe progression-free survival.
- 3. To describe changes in IMWG response for patients not in CR when initiating therapy with

- belantamab mafodotin as post-CAR-T maintenance.
- 4. To identify the rate of elimination of MRD ( $<10^{-5}$ ) in patients with myeloma at baseline and after starting belantamab mafodotin as post-CART maintenance (at screening/baseline, and after two, six, and 12 cycles).
- 5. Patient-reported quality of life studies (QoL).
- 6. To describe the overall survival for the entire cohort from the time of CAR-T administration.

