#### 2.4 **Secondary Endpoints**

- 1. Best objective response on the trial (by IMWG criteria).
- 2. Progression-free survival.
- 3. Negative MRD ( $\leq 10^{-5}$ , by clonoSEQ®), including imaging plus MRD-negativity ( $\leq 10^{-5}$  in bone marrow and no area of PET-CT FDG uptake greater than mediastinal blood pool or surrounding normal tissue.
- 4. Duration of response on maintenance.
- 5. Time to progression/relapse after CAR-T.
- 6. Overall survival for the entire study population.
- 7. Adverse events on the trial.
- 8. QoL parameters.

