For all subjects, disease evaluations will continue to be performed at least every 56 days (± seven days) until confirmed PD, death, start of a new anti-cancer treatment, withdrawal of consent, or loss to followup, whichever occurs first. Traditional efficacy assessment will be performed every cycle by serum protein electrophoresis and immunofixation and serum-free light chains, and after every two cycles by 24-hour urine protein electrophoresis and immunofixation. Minimal residual disease (MRD) assessment by next generation sequencing (clonoSEQ®), BCMA expression on bone marrow plasma cells and soluble BCMA/BAFF/APRIL will occur at screening and after two, six, and 12 cycles of belantamab mafodotin maintenance (refer to correlative schedule). In case of PD, subjects will be followed to ascertain subsequent anti-cancer therapy, if any, and survival status every six months (± 30 days) until withdrawal of consent, lost to follow-up, death, or the end of the study. Patients who discontinue treatment prior to progression will continue standard-of-care follow-up every three months until progression or start of another treatment (whichever comes first), then they will continue to long-term follow-up.

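### The planned summaries of MRD-negative prevalence and best response do not identify the MRD elimination rate or the response change that the secondary objectives ask for

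*Combined protocol and SAP*

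**What the plan says.** The objectives are worded as change. Section 2.3 has "To identify the rate of elimination of MRD", at screening/baseline and after two, six and 12 cycles. The Protocol Summary has "To describe changes in International Myeloma Working Group (IMWG) response category for patients not in CR when initiating therapy".

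The endpoints in Section 2.4 are worded as status: MRD-negative at 10^-5 or below, and best objective response on the trial by IMWG criteria. The analysis text follows the endpoints. Under Secondary outcomes in Section 8.2.5, "Best objective response on the trial and negative MRD prevalence at specific timepoints will be summarized as counts with percentages".

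Four other provisions matter:

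- Section 3.1 says MRD assessment "will occur at screening and after two, six, and 12 cycles of belantamab mafodotin" maintenance, so a pre-treatment value is collected.
- Section 4.6 requires at least SD after CAR-T and excludes CR/sCR at enrollment and again before the first dose. It does not exclude MRD-negative patients.
- Note 16 to the study calendar limits the MRD assay to patients in whom a trackable clone was identified.
- Section 8.2.4 assigns the efficacy population to the primary efficacy analysis and names no population for the secondary efficacy outcomes.

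**The concern.** Elimination is an event in a patient who was MRD-positive beforehand, and a change in response is measured against that patient's own starting category. The planned tables condition on neither. A patient whom CAR-T made MRD-negative before the first dose counts as negative at every later timepoint while that status lasts. A patient who enters in VGPR and stays there may count as a best response of VGPR.

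The plan does not define conversion, restrict the MRD summary to patients positive at screening, or provide a shift table. It also does not say whether IMWG response is measured from the pre-CAR-T or the pre-maintenance value. The starting category is recognised as relevant, but Section 8.2.5 uses it (PR or less versus VGPR) only to split the primary outcome.

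What is at stake is whether two stated objectives are answered, and whether the denominator is fixed before results are seen.

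**Working it through.** The plan gives no target or precision for either outcome, so there is no stated figure to reproduce. The check asks what the planned tables can reveal.

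**Inputs.** N = 45 (Section 8.1). The share MRD-negative at screening is not given; I assume 20% to 80%. Data are taken as complete, so that drop-out plays no part.

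**No conversions and no loss of negativity.** Later prevalence equals the screening share: 9, 18, 27 or 36 of 45 (20%, 40%, 60%, 80%). Elimination is 0% in every case.

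**What two prevalences allow.** Let B be the number negative at screening and F the number negative later. Among the 45 − B patients positive at screening, the number of converters lies between max(0, F − B) and min(45 − B, F).

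| B | F | Positive at screening | Fewest converters | Most converters | Range |
|---|---|---|---|---|---|
| 27 | 31 | 18 | 31 − 27 = 4 | min(18, 31) = 18 | 22% to 100% |
| 9 | 16 | 36 | 16 − 9 = 7 | min(36, 16) = 16 | 19% to 44% |

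The lower bound is exact if nobody loses negativity. The upper bound in the first row needs 14 of the 27 baseline-negative patients to have lost it (18 + 13 = 31, and 27 − 13 = 14). The planned table does not show where between these the truth lies.

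**Response.** Assume categories are measured from the pre-CAR-T value, and a start of 20 VGPR and 25 at PR or less. Let best response be 10 CR, 20 VGPR and 15 at PR or less, with no downward moves. Ten patients left the lowest group (25 − 15). If k of the 10 CRs came from VGPR, the number who moved up is 10 + k, with k from 0 to 10. So between 10 and 20 patients improved. The 10 CRs are known to be new; the remainder is not identified.

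**Precision of a conversion rate.** At about 40% conversion, exact 95% intervals are:

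| Negative at screening (assumed) | Positive at screening | Converted | Exact 95% CI |
|---|---|---|---|
| 20% | 36 | 14 | 23% to 57% |
| 40% | 27 | 11 | 22% to 61% |
| 60% | 18 | 7 | 17% to 64% |
| 80% | 9 | 4 | 14% to 79% |

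**The case against.** The strongest reply is that the objectives are partly answered already. Nobody may start study drug in CR/sCR, so any CR/sCR on study is new. The MRD objective lists screening among its timepoints, so the specific timepoints in Section 8.2.5 very likely include it. Baseline prevalence would then stand beside later prevalence, and with no conversions, no losses and complete data the series would be flat. All of this stands. It would be wrong to say that the plan cannot answer these objectives: net change in MRD, bounds on elimination, and new CR/sCR can be read from it.

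The outcomes are also descriptive, with no hypothesis or decision rule attached, and a conversion table could be produced later from the same data. That limits the weight of the point. It does not supply the missing definition, and a denominator chosen after results are seen is weaker.

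A reader might infer two stronger claims that the documents do not support.

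- **That prevalence will rise without any drug effect as MRD-positive patients leave.** This needs a denominator of patients still sampled, which the plan does not state, and retention rates, which it does not give. Suppose 75% of negatives and 45% of positives are retained, with no conversions. Screening shares b of 30%, 40% and 60% then read as 42%, 53% and 71% from 0.75b / (0.75b + 0.45(1 − b)). With all treated patients as denominator, the same retention gives 0.75b = 22.5%, 30% and 45%, a fall.
- **That nearly all patients will enter MRD-negative.** Section 1.2 reports, of 16 "patients with a response who were evaluated for MRD, 15 were MRD negative at" 10^-5. Those were evaluated responders in a study with a 45% CR rate. This trial excludes CR/sCR and admits SD. The figure shows that CAR-T alone can produce MRD negativity; it does not estimate the share here.

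**Conclusion.** The objectives ask for within-patient change and the analysis text gives marginal status. Followed as written, the plan does not identify the MRD elimination rate or the response shift below CR. The size depends on the screening MRD-negative share, which is unknown. At an assumed 60%, a rise from 27 to 31 of 45 is compatible with conversion anywhere from 22% to 100%; at an assumed 20%, a rise from 9 to 16 of 45 gives 19% to 44%. For response, the gap is confined to VGPR and below, and arises only if categories are carried over from a pre-CAR-T reference value.

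This should be corrected before results are seen, but it concerns descriptive secondary outcomes. The primary analysis is unaffected.

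**What to change.** In Section 8.2.5:

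1. Report the proportion converting to 10^-5 or below after cycles 2, 6 and 12 among treated, assay-informative patients who were MRD-positive at screening. Fix the denominator, count progressed, stopped or missing as not converted, and give an exact confidence interval.
2. Keep prevalence as a supportive summary, with the screening value shown and the denominator stated.
3. Add a shift table from the cycle 1 day 1 category to the best on-study category.
4. State whether IMWG response is measured from the pre-CAR-T or the pre-maintenance value.

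The cost is analysis text and two tables. MRD at screening and on treatment, and disease markers at cycle 1 day 1 and each later cycle, are already scheduled. The statistical price is precision: with 18 patients positive at screening, 7 conversions give an exact 95% interval of 17% to 64%. Counting missing as not converted is a conservative choice and should be labelled so.

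The new tables will not establish attribution. A single arm cannot separate the drug from a continuing CAR-T effect; Section 1.2 cites detectable CAR-T cells in 57% of patients at six months and 20% at 12 months. The results should be described as change on maintenance.

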#### Safety analyses

Safety analyses will be performed on the entire safety population. The incidence of severe adverse events will be reported for all subjects who received at least one dose of the study treatment. The proportion of patients experiencing an SAE will be reported overall, as well as classified by grade and organ system.

Formal toxicity monitoring will be performed for the following adverse events:

- SAEs that are possibly, probably or definitely related to treatment, with 30% acceptable rate
- Treatment-related grade 4 or higher non-hematologic toxicity, with 10% acceptable rate
- Grade 4 corneal adverse events, with 5% acceptable rate

Treatment-related death, i.e., grade 5 hematologic or non-hematologic toxicity, with 3% acceptable

The monitoring rules will suggest stopping the study when there is sufficient evidence that the proportion of patients with a specific adverse event exceeds the acceptable rate. Specifically, a Bayesian toxicity monitoring approach will be used, recommending stopping if the posterior probability of the event rate exceeding the acceptable rate is at least 80%. A Beta distributed prior with effective sample size of 1 and prior mean equal to the acceptable event rate was used for each event.

The tables assume that monitoring will be conducted after every five patients. Table 6 shows the cutoffs for the number of events that would trigger a stopping rule. For example, the third row shows that if 15 patients have been enrolled and 3 or more treatment-related non-hematologic AEs have occurred, then there is evidence to indicate that the proportion of these AEs exceeds the acceptable rate of 10%.

Table 6. Cutoffs for the number of patients with a specific adverse event indicating excessive rate of adverse event as a function of number of subjects in the study.

Subjects	Outcome			
	Treatment- related SAE (30%)	Treatment- related grade 4+ non-hematologic AE (10%)	Grade 4 corneal AE (5%)	Treatment- related death (3%)
5	≥ 3	≥ 2	≥ 2	≥ 1
10	≥ 5	≥ 3	≥ 2	≥ 2
15	≥ 7	≥ 3	≥ 2	≥ 2
20	≥ 8	≥ 4	≥ 3	≥ 2
25	≥ 10	≥ 5	≥3	≥ 2
30	≥ 12	≥ 5	≥ 3	≥ 3
35	≥ 13	≥ 6	≥ 4	≥ 3
40	≥ 15	≥ 6	≥ 4	≥3
45	≥ 17	≥ 7	≥ 4	≥3

Table 7 shows the operating characteristics of the boundaries listed in Table 6 for several values of true underlying probability of the adverse event. For example, if the true proportion of treatment-related SAEs is 40%, then the monitoring rule will be triggered over 83.6% of the time.

Table 7. Overall probability of crossing the boundaries defined in Table 6 with up to 45 subjects as a function of the underlying probability of the adverse event (cells with extremely low or high probabilities are left empty for clarity).

Underlying	Outcome (acceptable rate of adverse events)			
probability of event	Treatment- related SAE (30%)	Treatment- related grade 4+ non-hematologic AE (10%)	Grade 4 corneal AE (5%)	Treatment- related death (3%)
2%	-	0.6%	4.9%	16.9%
3%	-	1.7%	11.3%	28.9%
5%	0.1%	6.2%	29.7%	52.9%

Short Title: MCW EMBRACE TRIAL 66 Version Date: 12/29/2022

7.5%	0.4%	17.4%	55.0%	75.7%
10%	1.0%	33.8%	75.0%	88.9%
20%	9.8%	90.0%	99.1%	99.8%
30%	42.4%	99.6%	-	-
40%	83.6%	-	-	-
50%	98.6%	-	-	-

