#### 8.3 Accrual Estimates

MCW is required (per MCW sIRB) to activate prior to other sites, whose activation times will vary due to internal activation timelines. Accrual is expected at one subjects/month during year 1, and two subjects/month afterwards. Therefore, enrollment is expected to last 29 months; last subject, last dose and assessment are expected to take another 11 months. Therefore, total trial duration would be approximately 40 months.

The study will reach study completion in approximately 10 years (five years for completion of treatment for all patients, and five years of long-term survival follow-up) from the time the study opens to accrual.

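### Table 6 gives stopping cutoffs only at every fifth patient, and the plan does not say that the recommendation is triggered once the next look's cutoff has already been reached

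*Combined protocol and SAP*

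**What the plan says.** Section 8.2.5, Safety analyses, monitors four outcomes, each against its own acceptable rate: SAEs judged at least possibly related to treatment (30%), related non-hematologic toxicity of grade 4 or worse (10%), corneal events of grade 4 (5%), and deaths attributed to treatment (3%).

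The rule is advisory: "recommending stopping if the posterior probability of the event rate exceeding the acceptable rate is at least 80" per cent. On the prior: "A Beta distributed prior with effective sample size of 1 and prior mean equal to the acceptable event rate was used for each event". On timing, the only statement is "The tables assume that monitoring will be conducted after every five patients". Table 6 lists cutoffs at 5, 10, ..., 45 subjects, and Table 7 gives the overall crossing probabilities for that schedule.

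Three other sections bear on what happens between looks. Section 6.3 sends all grade 4 and 5 SAEs, and any other SAE reported on an expedited basis to the IRB, to the DSMC within five calendar days. Section 10.4 lets the DSMC terminate an unsafe study and sets its routine review at no less than twice a year. Section 4.11 allows several bodies to suspend the study for reasonable cause. None of these refers to Table 6.

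Section 8.3 gives the pace of enrolment: "Accrual is expected at one subjects/month during year 1, and two subjects/month afterwards".

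**The concern.** The quantity being monitored is a count of patients who have had an event, and such a count only rises. Once it equals the cutoff for the coming look, no later data can prevent the crossing at that look. The plan's own posterior criterion is also already met, because the same count in fewer patients gives a higher posterior probability.

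Waiting for the scheduled look therefore adds no information about whether the boundary will be crossed and gives no extra protection against false stopping. It only means that more patients may enter before the recommendation is made. At the planned accrual, four patients take about four months in year 1 and about two months later.

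**Working it through.** **Inputs.** Acceptable rates p0 of 30%, 10%, 5% and 3%, the 80% criterion, a Beta prior with effective sample size 1, looks at 5, 10, ..., 45 (all from Section 8.2.5), and the Table 7 crossing probabilities.

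**Step 1: reproduce Table 6.** The prior is Beta(p0, 1 − p0). With r events in n patients the posterior is Beta(p0 + r, 1 − p0 + n − r). The cutoff is the smallest r for which P(rate > p0) is at least 0.80. All 36 cutoffs match.

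**Step 2: reproduce Table 7.** An exact binomial recursion, patient by patient to n = 45 with stopping at the nine looks, matches every filled cell to rounding. At the acceptable rate it gives 42.36% (SAE), 33.84% (grade 4+ non-hematologic), 29.72% (corneal) and 28.86% (death), against 42.4%, 33.8%, 29.7% and 28.9% in the table.

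**Step 3: declare a crossing as soon as the count equals the next look's cutoff.** A path that reaches this point early must cross at the look, and a path that crosses at the look must have reached it by then. The two sets of paths are the same, and the recursion confirms identical probabilities in every Table 7 cell. Only the timing changes:

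| Outcome, true rate | Crossing probability, both rules | Mean patients at crossing, scheduled look | Mean patients at crossing, next cutoff reached | Difference |
|---|---|---|---|---|
| Death, 10% | 88.89% | 15.0 | 13.0 | 2.0 |
| Grade 4 corneal, 10% | 74.98% | 19.4 | 17.6 | 1.8 |
| Grade 4+ non-hematologic, 20% | 90.00% | 16.0 | 14.5 | 1.5 |
| Treatment-related SAE, 40% | 83.61% | 14.9 | 14.1 | 0.8 |

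Means are among trials that cross. Over all the rates in Table 7, the mean difference is 1.9–2.3 patients for death, 1.7–1.9 for corneal, 1.2–1.6 for grade 4+ non-hematologic and 0.5–0.9 for SAE.

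**Step 4: longest wait.** A trial that passes one look with cutoff c has at most c − 1 events. If the next cutoff is c′, it needs c′ − c + 1 more events, so the longest wait is 5 − (c′ − c + 1) = 4 − (c′ − c). In the first block it is 5 minus the first cutoff.

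- SAE cutoffs always rise by 1 or 2 between looks, so the longest wait is 4 − 1 = 3 (first block: 5 − 3 = 2).
- Grade 4+ non-hematologic and corneal cutoffs repeat at some consecutive looks, so the longest wait is 4 − 0 = 4.
- Death has a first cutoff of 1, giving 5 − 1 = 4, and its later cutoffs also repeat.

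**Step 5: worked example.** One grade 4 corneal event occurs among patients 1–5 and a second in patient 6.

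- At n = 5, with r = 1: Beta(1.05, 4.95) gives P(rate > 5%) = 79.5%, just short of 80%, so there is no crossing (cutoff 2).
- At n = 6, with r = 2: Beta(2.05, 4.95) gives 97.1%. The n = 10 cutoff of 2 is met with four patients still to come.
- At n = 10, if none of those four has an event: Beta(2.05, 8.95) gives 92.1%, so the boundary is crossed whatever happens in between.

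**Step 6: contrast with recalculating the 80% rule after every patient.** This is a different rule and it does change error control. The probability of stopping at the acceptable rate rises as follows (in brackets: recalculation starting at patient 5):

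- SAE: 42.4% to 61.6% (51.3%);
- grade 4+ non-hematologic: 33.8% to 46.6% (40.9%);
- corneal: 29.7% to 38.5% (31.7%);
- death: 28.9% to 32.8% (32.8%).

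**The case against.** **Looks every five patients are a disclosed choice with reported operating characteristics.** This stands. Tables 6 and 7 are correct and contain no contradiction. The plan states the five-patient schedule as an assumption of the tables and nowhere forbids review in between, so a reader who infers that the boundaries may be checked only at every fifth patient goes further than the text. The supportable point is that the operational schedule, and what happens between looks, is not stated.

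**Serious events reach the DSMC anyway.** A reader might picture two treatment-related deaths among the first six patients going unexamined until patient 10. The documents do not support that. At least one of those deaths is among the first five patients, so the n = 5 cutoff of 1 would already have been met unless that death came to light after that look. Each death would also go to the DSMC within five calendar days under Section 6.3, and Sections 4.11 and 10.4 provide for suspension or termination. This softens the practical effect considerably. It does not remove it, because these reviews are discretionary and are not linked to the boundaries. Related SAEs below grade 4 that need no expedited IRB report count toward the 30% boundary but fall outside the five-day rule.

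**The savings assume immediate outcomes.** This also stands. Treatment runs for up to twelve 56-day cycles and adverse events are collected to 70 days after the last dose, so events in early patients may surface after later patients have enrolled. The means in the table describe the model behind Table 7 and are not forecasts for this trial.

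**The effect is modest.** It is, particularly for SAEs, where the mean difference at a true rate of 40% is 0.8 patients.

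**Conclusion.** The point holds as a gap in the rule that can be closed at no statistical cost. When the count has reached the next look's cutoff, the recommendation is certain, and waiting gains nothing in error control. The longest wait is four patients for three of the outcomes and three for treatment-related SAEs. The mean among crossing trials is between about 0.5 and 2.3 patients, depending on outcome and true rate.

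The certainty of crossing requires only that an event, once counted, is not later reclassified. The patient savings also require each outcome to be known before the next patient is counted.

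Two stronger conclusions might be drawn, and neither follows. The first is that the 80% rule should be applied after every patient; Step 6 shows that this raises false stopping and would invalidate Table 7. The second is that reaching the cutoff should automatically halt dosing. The plan's rule only recommends stopping and has no such hold even at a scheduled crossing. Table 7 gives a 28.9% to 42.4% chance of crossing when the true rate equals the acceptable rate, so unchanged crossing probabilities do not justify an automatic halt.

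**What to change.** Add one sentence to Section 8.2.5 after the description of the rule:

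*A Table 6 boundary is considered crossed, and the stopping recommendation is sent to the DSMC, as soon as the number of patients with the event equals the cutoff for the next scheduled look.*

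In the same place, state outright that the scheduled looks are at 5, 10, ..., 45 patients, so that the schedule is no longer only an assumption of the tables. Do not word the change as a recalculation of the posterior after each patient. Leave any action on enrolment or dosing to the sponsor and DSMC.

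The cost is the added text and a running count of patients with each event. SAEs already have to be reported to the coordinating team within 24 hours under Section 6.3, and non-hematologic grade 4 events that are not SAEs under Section 6.4. Cutoffs, crossing probabilities and sample size do not change.
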